Evaluation of the Safer Bars Prevention Program for Sexual Assault

NCT: 04141839

Date: March 13, 2025

Study Protocol and Statistical Analysis Plan

Study Protocol

The objectives of the protocol are to conduct a cluster-randomized controlled trial with crossover, multiple sources of data, and a theory-driven analysis plan to assess the immediate and intermediate effectiveness of *Safer Bars*, a primary perpetration prevention program to train bar staff to recognize and respond to sexual aggression and its precursors among patrons. This prospective evaluation will assess individual-level outcomes, including changes in bar staff members' attitudes, perceived social norms, perceived behavioral control, behavioral intent, and subsequent bystander behavior. Bar-level outcomes will include changes in the physical bar environment and risk management safety policies. Additionally, we will use GIS mapping to identify "hot spots" of liquor licenses in areas within a 3-mile radius of the three major Arizona universities and map police dispatches for reports of sexually-violent behavior in these areas prior and subsequent to the intervention in order to assess community-level outcomes.

Recruitment. The study will recruit approximately 56 bars with an average of ten participants per bar for an intended sample size of 564 individual bar staff and 56 bar owners/managers. Sampling of bars will be proportional to the size of student enrollment at each of the universities. The study will sample from bars that are located within 3 miles of the university campuses, have a current liquor license to serve on-premises, and have not received the *Safer Bars* training within the past year.

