Project staff will generate a list of bars in the catchment areas and will contact their owner/managers through combinations of email, phone, social media, and in-person visits. If a bar owner/manager is interested in receiving more information, staff will describe the training and study, as well as provide informational material. If a bar agrees to participate, the owner/manager will sign the Bar Agreement Form, which details the time commitment and study details. Project staff will then utilize a block randomization procedure to determine which arm (control or intervention) the bar is in and will convey this to the owner/manager as well as details about the monetary incentive (\$250) available to cover some of the costs of hosting the study at their establishment. Research staff may also recruit through organizations or associations related to bartending, bartenders, or bar owner/managers within the specified catchment areas. Bars may receive *Safer Bars* training without participating in the study.

Before training session 1 (intervention group) or the information session (control group), research staff will meet with the bar owner/manager to review the consent form and screening questions. If the bar owner/manager is eligible and agrees to participate, they will provide informed consent and their contact information. At the beginning of training session 1 (intervention group) or the information session (control group), staff will discuss the study with the bar staff, provide them the opportunity to ask questions, assess eligibility, and obtain informed consent and contact information. Individuals who do not wish to participate in the study may still attend the training.

Retention. We will take multiple steps to retain participants throughout the project. First, we will make participation as convenient as possible by using in-person data collection for the baseline surveys and online data collection for the follow-up surveys. Second, we will give reminders to participants regarding survey completion. Finally, we will structure our payment and incentive schedule to encourage full completion.

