Violent crime datasets will be obtained from relevant municipal police departments via public records requests for years prior to and during the study. Maps will be generated using ArcGIS ArcMap. Violent crimes of interest will be mapped using the "Esri World Geocoder" under the "Geocode Addresses" tool and then shapefile layers will be created.

Next, spatial information of the liquor licenses for the relevant bars will be obtained from the Arizona Department of Liquor Licenses and Control (DLLC) website. Only "on-premises" liquor license addresses will be queried and mapped. Shapefile layers of bar locations will be created and added to the maps. Utilizing the "Kernel Density" tool within the "Spatial Analyst

Toolbox" via ArcMaps, bar location density will be mapped against the crime points. The results will illustrate the amount of violent crime in a specific location in relation to the density of bars for that exact location. Analyses will compare the frequency of violent crime-related police dispatches to study catchment areas before and after receiving *Safer Bars* training.

Power Analysis

The sample size of 564 individual bar staff (approximately 56 bars [28 bars in each study arm] x average of 10 participants per bar) affords power of .80 to detect small-to-moderate standardized between-group differences (i.e., intervention effects) on individual-level outcomes ranging from d = 0.28 to 0.45, depending on an assumed intraclass correlation (ICC) of .10 for outcome scores, assumed correlations between baseline and follow-up scores ranging from r = .10 to .50, and assumed ICCs for pre-post change scores ranging from .05 to .10. Adjusting for bar-level clustering, the proposed sample should afford power of .80 to detect indirect effects and small-to-moderate constituent direct effects (ds= 0.35-0.45 for X to M, r2s = .04-.09 for M to Y), assuming a 10% attrition rate. For bar-level outcomes, the proposed sample size affords power to detect large effects (ds = 0.66-0.76, for pre-post correlations of r = .10-.50).

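### The catchment before/after comparison of police dispatches has no control for background change and no defined windows, so it can describe change but not attribute it to the program

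*Combined protocol and SAP*

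**What the plan says.** The objectives paragraph of the Study Protocol sets out to "assess the immediate and intermediate effectiveness of" the program. Later in the same paragraph it adds that police dispatches near the three universities will be mapped "prior and subsequent to the intervention in order to assess community-level outcomes".

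The SAP section on Community-level Analyses names two outputs. One is a kernel-density map of bar density against crime points, which contains no training variable. The other is the only one that involves the program: "Analyses will compare the frequency of violent crime-related police dispatches to study catchment areas before and after receiving" the training. No arm, comparison area, trend or season term, model or denominator is given. The crime data are requested for an unstated number of years before the study and for the study itself. That describes the data request and does not define comparison periods.

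Three other parts of the plan bear on this:

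- **Recruitment, sampling.** All bars, whichever arm they enter, lie within 3 miles of a campus, and "Sampling of bars will be proportional to the size of student enrollment at each of the universities".
- **Recruitment, allocation.** The arm is set bar by bar: "Project staff will then utilize a block randomization procedure to determine which arm" a bar enters. Bars may also have the "training without participating in the study", and the exclusion for earlier exposure covers only "training within the past year".
- **Study Design.** Waitlist bars become eligible for the intervention after 3 months.

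**The concern.** Randomization protects a comparison between bars. It does not protect a comparison of a whole catchment with its own past. Dispatch totals can move with policing, reporting, enrollment, season or longer trends, and nothing in the planned comparison separates these from the program. Because bars of both arms sit in the same areas, a catchment also has no obvious single date that divides before from after. With the windows left open, they could be chosen after the data are seen. At stake is whether a rise or fall in dispatches could be presented as community-level evidence that the program works or fails.

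**Working it through.** The documents state no count, effect size, alpha or power for the community outcome. The Power Analysis covers individual-level, indirect and bar-level effects only. There is no figure to reproduce, and every dispatch input below is an assumption.

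**1. How many training dates does a catchment have?** The plan has about 56 bars, 28 per arm, at three universities. Since 56/3 = 18.7, at least one catchment holds 19 or more bars. Under a random 28 v 28 split without strata (block size and strata are not given), the chance that all k bars of a catchment fall in one arm is 2 × C(28,k)/C(56,k):

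- k = 3: 2 × 3,276/27,720 = 0.236
- k = 5: 2 × 98,280/3,819,816 = 0.051
- k = 10: 0.0007
- k = 19: 3 × 10⁻⁸

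If allocation were blocked within campus, mixing would be more certain still. Immediate and waitlist bars therefore almost surely share the larger catchments. No calendar dates are given, so several training dates per catchment is an inference, though a strong one.

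**2. How large a signal could the catchment total carry?** Let s be the share of catchment dispatches that arise near study bars, 0.70 the assumed rate ratio there, and b the background change. Then observed change = (1 + b)(1 − 0.30s) − 1.

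| s | b = 0 | b = −5% | b = +5% |
|---|---|---|---|
| 5% | −1.5% | −6.43% | +3.43% |
| 10% | −3.0% | −7.85% | +1.85% |
| 20% | −6.0% | −10.7% | −1.3% |

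At 5% or 10% the program's contribution is smaller than a 5% background shift, and a 5% rise reverses the sign. The sign holds only if s exceeds (1 − 1/1.05)/0.30 = 0.159, about 16%.

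**3. What would an obvious window choice leave?** One natural reading is before the first and after the last study-bar training. The last planned assessment is 6 months post-intervention, and waitlist bars become eligible at 3 months. If the last bars to enter include controls, about 6 − 3 = 3 months of in-study data remain after the last training, against years before it. A 3-month window set against whole years is also unbalanced by season.

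**4. Could a better model rescue the outcome?** A model of quarterly dispatches near each bar, with the bar's own training date as exposure plus bar and quarter effects, was simulated with 400 runs per cell. Assumptions: 56 bars; 16 quarters; entry spread over quarters 5-12; controls trained one quarter after entry; a 5% yearly fall; a ±15% season; between-bar gamma variance 0.5; bar-by-quarter lognormal variance 0.2 with autocorrelation 0.5. At 0.5, 1 and 2 dispatches per bar per quarter:

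- rate ratio 1: mean estimate 1.00-1.02; type I error 0.07, 0.05, 0.06
- rate ratio 0.70: power 0.34, 0.52, 0.71
- rate ratio diluted to 0.85: power 0.13, 0.19, 0.24

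The model handles the background change in this setting, but its power is low.

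**The case against.** The strongest reply is that this is mapping and not inference. The community sentence in the objectives follows the effectiveness objective as an addition. The SAP section speaks of maps and illustration, and no test, alpha or power is attached. That is a fair reading, and it limits the point: a reader might infer that the plan will declare a program effect from a significant before/after change, but the documents plan no such test and state no such rule. The reply does not remove the point, because the SAP never says the comparison is descriptive and the objectives present it as part of an evaluation of effectiveness.

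A second reply is that a bar-level model would be weak and still exposed to spillover. That stands, so such a model can only be optional and supportive.

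Third, training before or outside the study is allowed by the plan but not documented as having happened. A reader might infer contaminated baselines; the documents show only that they are possible.

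Finally, the objectives refer to sexually violent behavior and the SAP to violent crime. That difference in outcome definition is a separate matter and is not needed here.

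**Conclusion.** The point holds, and the plan should address it. Followed as written, the catchment comparison mixes background change with any program effect and leaves its periods open, so it cannot count as evidence of effectiveness. The size is illustrative: with study bars at 5-10% of dispatches and a rate ratio of 0.70 near them, the total moves by 1.5-3%. At an assumed share of 20% it moves by 6%, slightly more than a 5% background shift, but even then the two cannot be told apart without a control for time.

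A reader might infer that the trial's main conclusions are compromised. They are not: the SAP analyzes the individual-level and bar-level outcomes by study arm with baseline adjustment, and neither depends on this comparison. That the comparison is uncontrolled and its windows undefined follows directly from the text. The presence of several training dates per catchment is inferred from the design, and the percentages rest on assumed inputs.

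**What to change.** 1. State in Community-level Analyses that the catchment before/after maps and frequencies are descriptive and that no program-effect conclusion will be drawn from them. This costs one sentence.
2. Before analysis, fix before and after windows of equal length covering the same calendar months, and name the dates that anchor them in each catchment. Confirm that the police records requested cover the after window. The cost is wording, plus possibly an extended records request. Equal windows remove seasonal imbalance but not trend, so item 1 is still needed.
3. Optionally, if the records carry event dates (the SAP does not mention them), add a supportive count model of quarterly dispatches near each study bar. Use the bar's own training date as time-varying exposure, bar effects, calendar-quarter terms and bar-clustered standard errors. Report the estimate with its interval and no pass/fail test. Adding an arm term to the catchment total would not serve, because both arms share the catchments.

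Item 3 uses addresses and crime records already planned, together with session dates the trial should hold. The simulated 16-quarter series may need records beyond those planned. Its limits should be stated: counts near single bars may be sparse; power is about 13-24% for a ratio of 0.85 under the assumptions above; spillover remains; and only the 3-month offset between arms is randomized, not the dates on which bars enter. Items 1 and 2 are sufficient without it.

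### The community objective concerns dispatches for sexually violent behavior, but the SAP compares violent-crime dispatches without tying them to sexual violence, so an effect on the stated outcome may be diluted

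*Combined protocol and SAP*

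**What the plan says.** The opening objectives paragraph of the Study Protocol describes a program to "train bar staff to recognize and respond to sexual aggression and its precursors among patrons". For the community level it says the team will "map police dispatches for reports of sexually-violent behavior in these areas prior and subsequent to the intervention in order to assess community-level outcomes".

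The Community-level Analyses section of the SAP uses different terms at each step:

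- Data request: "Violent crime datasets will be obtained from relevant municipal police departments via public records requests for years prior to and during the study".
- Geocoding: "Violent crimes of interest will be mapped using the 'Esri World Geocoder".
- Map output: "The results will illustrate the amount of violent crime in a specific location in relation to the density of bars for that exact location".
- Comparison: "Analyses will compare the frequency of violent crime-related police dispatches to study catchment areas before and after receiving" the training.

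Sexual violence is not mentioned anywhere in that section. The Power Analysis section covers individual-level, indirect and bar-level effects. It gives no event count, effect size or power for the community analysis.

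**The concern.** The objective names one class of event and the analysis names a wider one. If the SAP is carried out as worded, dispatches for non-sexual violence are counted together with the dispatches that the objective is about. Two errors become possible. A real change in sexually violent dispatches can be hidden in a total that hardly moves. A change in other violence, from whatever cause, can be read as an effect of the training.

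The limiting phrase in the geocoding sentence carries no offence list or call codes. The choice of events could therefore be made after the data have been seen. This is the trial's only community-level outcome, so the wording decides whether that objective is answered at all.

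**Working it through.** **1. The text, side by side.**

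| Step | Event named | Limited to sexual violence? |
|---|---|---|
| Objective (Study Protocol) | Dispatches for reports of sexually violent behavior | Yes |
| Data request (SAP) | Violent crime | No limit stated |
| Geocoding (SAP) | Violent crimes of interest | Some limit implied, not defined |
| Map output (SAP) | Violent crime | No limit stated |
| Before/after comparison (SAP) | Violent crime-related dispatches | No limit stated |

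The only qualifier sits in the geocoding sentence. It is absent from the sentence that defines the comparison, and nothing in the document reconciles the two outcomes.

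**2. Inputs for an illustration.** The plan has no community-level figure to reproduce. Every number below is an assumption: sexual-offence share s from 5% to 50%; fall in sexually violent dispatches f = 30% (rate ratio 0.7); other violence unchanged; Poisson counts; equal periods before and after; two-sided α = 0.05; 1,000 violent-crime dispatches before (step 4 only).

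**3. Dilution.** The relative change in the total is f × s, so the rate ratio for the total is 1 − s × 0.3. At s = 10% it is 1 − 0.03 = 0.97. At s = 50% it is 1 − 0.15 = 0.85.

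**4. Simple z with 1,000 dispatches before.** z = difference / √(sum of the two counts).

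| s | Sexually violent only | All violent |
|---|---|---|
| 5% | 15/√85 = 1.63 | 15/√1985 = 0.34 |
| 10% | 30/√170 = 2.30 | 30/√1970 = 0.68 |
| 20% | 60/√340 = 3.25 | 60/√1940 = 1.36 |

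The numerator is the same in both columns. Only the noise grows.

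**5. Power, without fixing the count at 1,000.** For a Wald test on the log rate ratio, the events needed before training for 80% power are (1.96 + 0.84)² × (1 + 1/RR) / (ln RR)². With RR = 0.7 this is 7.85 × 2.429 / 0.1272, or about 150 sexually violent dispatches. The same areas and periods then hold N = 150/s violent-crime dispatches. Power on the total is Φ(|ln RR_total| / √(1/N + 1/(N × RR_total)) − 1.96). At s = 10%, N = 1,500, the standard error is 0.0368 and |ln 0.97| = 0.0305, which gives Φ(−1.13) = 13%.

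| s | RR for total | Power on total | Violent dispatches before needed for 80% |
|---|---|---|---|
| 5% | 0.985 | 8% | 69,246 |
| 10% | 0.970 | 13% | 17,182 |
| 20% | 0.940 | 22% | 4,232 |
| 30% | 0.910 | 31% | 1,853 |
| 50% | 0.850 | 48% | 647 |
| 100% | 0.700 | 80% | 150 |

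The loss hardly depends on the assumed effect. With rate ratios of 0.8 and 0.5, power is 13% and 12% at s = 10%, and 49% and 46% at s = 50%.

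**6. The opposite error.** With no program effect, a fall g in other violence moves the total by g × (1 − s). It matches the movement that a 30% fall in sexually violent dispatches would produce when g = 0.3s/(1 − s). That is 0.03/0.90 = 3.3% at s = 10%, 0.06/0.80 = 7.5% at s = 20% and 0.15/0.50 = 30% at s = 50%.

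**The case against.** The best defence is the qualifier in the geocoding sentence. It signals a selected subset, and the only subset named in the document is the sexually violent behavior of the objective. On that reading the section is loose shorthand: obtain a violent-crime file, extract the relevant offences, and count those. Then s is close to 100% and the dilution disappears. This reading is possible and cannot be excluded. It does not settle the matter, because the qualifier is undefined and is missing from the comparison sentence itself.

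Several stronger readings are tempting and should not be drawn:

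- A reader might infer that the analysis certainly counts all violent crime, or that non-target events would dominate the result. The qualifier speaks against the first. The second needs a sexual-offence share below one half, and the documents give no offence mix.
- A reader might infer that the data source has changed from dispatches to crime records. The SAP's comparison is still of dispatches, and the files requested could be dispatch files. The source is unclear, not shown to be different.
- A reader might infer that the program can affect sexual aggression only. The protocol also lists changes in the physical bar environment and in risk management safety policies as bar-level outcomes, and such changes could plausibly affect other violence.

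It is also fair to say that this is a mapping component with a one-sentence comparison, no stated test and no power claim. That limits the consequence to the community aim. It does not remove the mismatch.

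**Conclusion.** The point stands as a mismatch between objective and analysis. The objective is limited to sexually violent dispatches, and the comparison as worded is not. This is more than a missing detail, because the words that define the comparison describe a broader outcome than the objective does.

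The size cannot be fixed from the documents. What holds generally, if other violence is unchanged, is that the total moves by f × s and that adding the other events brings noise without signal. The power and z figures show direction and possible scale. They rest on assumed values for s, the 30% fall and, for z, the count of 1,000, with Poisson variation and stable other violence. Within those assumptions the loss is material even at s = 50%, and it is nil if the undefined subset turns out to be exactly the sexually violent dispatches.

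The change is worth making. The point is confined to the community aim and leaves the individual-level and bar-level analyses untouched. Whether a before/after comparison is adequate for this aim is a separate question.

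**What to change.** In the Community-level Analyses section:

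- State that the before/after comparison is of police dispatches for sexually violent behavior.
- Define that behavior by a list of call or offence codes for each police department, fixed before the data are seen. Use the same definition in the request, the geocoding, the maps and the comparison.
- State that the records requested are dispatch records.
- If other violent-crime dispatches are obtained, report them separately as context. They should not form part of the outcome, and they should not be labelled a negative control, since the documents do not establish that the program leaves them unaffected.

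The cost is a change of SAP wording and a more specific public records request. The drawbacks are smaller counts and the work of mapping codes across departments.

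### The only before/after comparison of police dispatches uses whole catchments, so an effect concentrated near trained bars is diluted to an unknown degree; a near-bar count should be added

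*Combined protocol and SAP*

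**What the plan says.** The opening objectives of the Study Protocol describe hot spots "of liquor licenses in areas within a 3-mile radius of the three major Arizona universities" and an intention to "map police dispatches for reports of sexually-violent behavior in these areas prior and subsequent to the intervention". Under Recruitment, "The study will sample from bars that are located within 3 miles of the university campuses", and the next paragraph adds: "Project staff will generate a list of bars in the catchment areas". The catchment is therefore the zone that holds all candidate bars, whether or not they join.

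Community-level Analyses in the SAP geocodes the crimes and maps on-premises licence addresses: "Shapefile layers of bar locations will be created and added to the maps". A kernel-density step then relates crime to licence density by location. The one sentence that compares periods reads: "Analyses will compare the frequency of violent crime-related police dispatches to study catchment areas before and after receiving" the training.

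Power Analysis gives the number of participating bars as "approximately 56 bars [28 bars in each study arm] x average of 10 participants per bar". Under Study Design, intervention bars are trained first, and waitlist bars become eligible only after a three-month wait.

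**The concern.** The place where events are counted does not match the place where the program acts. Training is delivered inside individual bars, while the count covers everything within three miles of a campus, including streets, homes and licensed premises that are not in the study. No section defines a distance around a participating bar or links an event to a bar.

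The dates do not match either. A catchment holding both intervention and waitlist bars has no single training date, so before and after are not well defined for it. They are well defined for each trained bar.

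What is at stake is how to read the community-level result. If the total does not move, the reader cannot tell a program without local effect from a local effect averaged with many unaffected events. Both sets of locations are already held as points, so the finer count is available and is simply not planned.

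**Working it through.** **Plan's own figure.** There is none to reproduce. Power Analysis covers individual-level outcomes, mediation and bar-level outcomes. No event count, rate or detectable difference is given for dispatches.

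**Inputs from the documents.** Counting unit: the catchment (Community-level Analyses). Catchment: within 3 miles of three campuses (objectives, Recruitment). Participating bars: about 56 (Power Analysis).

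**Assumptions, not in the documents.**
- s: share of catchment events arising near participating bars, taken as 5% to 50%.
- R: relative fall near those bars, taken as 20%.
- Poisson counts, equal periods, two-sided alpha .05, power .80.
- At first, the whole effect lies near the bars.

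**Step 1: dilution.** The catchment fall is s × R. For s = 10%, 0.10 × 0.20 = 2%.

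**Step 2: events needed.** With rate ratio RR = 1 − s × R, total events over both periods = (1.960 + 0.842)² × ((1 + RR)/(1 − RR))². The first factor is 7.8489. For s = 10%, RR = 0.98 and the total is 7.8489 × 99² = 76,927. Counting near bars only, RR = 0.80 and the total is 7.8489 × 9² = 636.

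These two totals count different events. On a common footing at s = 10%, the catchment design needs 76,927/1.98 = 38,852 events in the before period, of which 10%, or 3,885, are near bars. The near-bar design needs 636/1.80 = 353. The ratio is about 11.

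**Step 3: precision gain.** Suppose N events, of which sN are near bars, and a total fall of D events, of which a fraction f lies within the buffer. The signal-to-noise ratio is proportional to D/√N for the catchment and fD/√(sN) for the buffer. The near-bar count gains by f/√s, which is 1/√s when f = 1. The advantage is lost once f falls below √s.

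| Assumed s | Catchment fall if R = 20% | Total events needed, catchment | Gain at f = 1 (1/√s) | Break-even f (√s) |
|---|---|---|---|---|
| 5% | 1% | 310,823 | 4.5 | 0.22 |
| 10% | 2% | 76,927 | 3.2 | 0.32 |
| 30% | 6% | 8,206 | 1.8 | 0.55 |
| 50% | 10% | 2,833 | 1.4 | 0.71 |

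The result depends heavily on s, which the documents do not allow us to estimate.

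**The case against.** The strongest reply is that the objectives ask for community-level outcomes, and a catchment total measures those directly. That stands: the plan does not misanalyse its stated aim, and the totals should be kept. The SAP also names no test or decision rule for this comparison, so it may be meant as description, and records covering several years could yield many events.

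The kernel-density step does keep location. However, it is described as illustrating crime against licence density. It is not said to separate participating from other bars, or trained from untrained ones, so it does not fill the gap.

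Three stronger readings are tempting, and the documents do not support them:
- **A local effect would be undetectable, and a null result would say nothing.** That depends on s and on event counts, neither of which is given. With large s and many events, a local effect could show in the total.
- **The rest of the catchment is beyond the program's reach.** Recruitment allows bars outside the study to be trained, so some effect elsewhere is possible, though the analysis does not track it.
- **Area measures the dilution.** Three 3-mile circles cover 3 × π × 3² = 84.8 square miles, and quarter-mile circles around 56 bars at most 56 × π × 0.25² = 11.0, or 13%. But dispatches may cluster near bars, so a share of area is not a share of events.

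Objections to the remedy also stand in part. Any radius is a choice the documents do not inform, a buffer still contains unrelated premises, neighbouring buffers may overlap, and events that occur after patrons move away are missed.

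**Conclusion.** The concern holds as one of attenuation of unknown size. The only before/after comparison is by catchment, while training reaches individual bars at different times. An effect confined to their surroundings is multiplied by s in the total: a 20% fall becomes 1%, 2% or 6% at assumed s of 5%, 10% or 30%. A null catchment result would then be weak evidence about the program. It would not be empty evidence.

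The gain from a near-bar count is 1/√s at best and f/√s in general, under Poisson variation. This is a cheap improvement to a secondary analysis. It leaves the individual-level and bar-level results untouched. It also does not make the community analysis causal: an uncontrolled near-bar comparison of periods would still need a comparator.

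**What to change.** Keep the catchment totals for the community-level aim. Add to Community-level Analyses a second, prespecified count that states:
- the distance around each participating bar and one sensitivity distance (a quarter mile and a tenth of a mile would serve as examples), fixed before dispatch data are examined;
- before and after periods set by that bar's own training date, with their lengths, and how a waitlist bar that never takes up training is handled;
- a rule that assigns an event inside overlapping buffers to one bar, for example the nearest;
- that the near-bar comparison of periods alone will not be read as attributable to the program.

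The cost is SAP wording and one buffer step in GIS software already in use, on points already geocoded. No new data collection is needed. The price is smaller counts per bar, an arbitrary radius (hence the sensitivity distance) and missed events farther away, for which the retained catchment totals remain the check.

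### The individual-level detectable effects are stated for all 564 enrolled staff, without the 10% attrition assumed for mediation; applying it moves the lower end from 0.28 to about 0.295.

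*Combined protocol and SAP*

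**What the plan says.** The Recruitment section of the protocol plans for "an average of ten participants per bar for an intended sample size of 564 individual bar staff", and Study Design repeats that number as the one randomized. The Power Analysis section of the SAP builds on it: "The sample size of 564 individual bar staff (approximately 56 bars [28 bars in each study arm] x average of 10 participants per bar". It says this sample "affords power of .80 to detect small-to-moderate standardized between-group differences (i.e., intervention effects) on individual-level outcomes ranging from d = 0.28 to 0.45". The inputs it lists are an ICC of .10 for outcome scores, baseline to follow-up correlations of .10 to .50, and ICCs of .05 to .10 for change scores. Attrition is not among them.

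The next sentence concerns indirect effects and their component paths, and ends "r2s = .04-.09 for M to Y), assuming a 10% attrition rate". This is the only attrition rate in the document. Nothing says that 564 was inflated for dropout.

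Under Individual-level Analyses, the main test of the program is a mixed model for bystander behavior at follow-up, adjusted for baseline behavior, with a random intercept for bar. The mediation models predict the same behavior prospectively.

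**The concern.** Two adjacent power statements about the same recruits rest on different samples. A person who does not return the follow-up survey is missing from the program-effect analysis as well as from the mediation analysis, so a 10% loss expected for one should be expected for the other. As written, the sensitivity of the main individual-level comparison is given for a sample that the plan does not expect to have at follow-up. Someone interpreting a null result would take the lower figure, 0.28, as the smallest effect covered at .80 power under the most favourable inputs.

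**Working it through.** **Inputs from Power Analysis:** 56 bars, 28 per arm; N = 564, so m = 564/56 = 10.07 staff per bar; power .80; r = .10 to .50; ICC .05 to .10; attrition 10%. **Assumed:** alpha .05 two-sided, since none is given for these outcomes; loss spread evenly within bars, so that all 56 remain.

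**Formulas.** Design effect DE = 1 + (m − 1) × ICC. SE = √(4 × V × DE / N), where V = 2(1 − r) for a change score and V = 1 − r² for a baseline-adjusted comparison. Detectable d = (1.960 + 0.842) × SE. Power at d = Φ(d/SE − 1.960). The t variant uses the noncentral t with 56 − 2 = 54 df.

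**Step 1: reproduce the stated range, N = 564, change score.**
- Lower end, r = .50, ICC .05: V = 1; DE = 1 + 9.07 × .05 = 1.454; SE = √(4 × 1.454/564) = 0.1015; d = 0.284. Power at 0.28 is Φ(0.80) = 0.79.
- Upper end, r = .10, ICC .10: V = 1.8; DE = 1.907; SE = √(4 × 1.8 × 1.907/564) = 0.1560; d = 0.437.
- By t the two ends are 0.290 and 0.445.

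The 0.28 end matches by z. The 0.45 end is matched a little more closely by t.

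**Step 2: apply the plan's 10%.** N = 0.9 × 564 = 507.6; m = 507.6/56 = 9.06.
- Lower end: DE = 1.403; SE = √(4 × 1.403/507.6) = 0.1052; d = 0.295. Power at 0.28 is Φ(0.70) = 0.76. By t: d = 0.300, power 0.74.
- Upper end: DE = 1.806; SE = √(4 × 1.8 × 1.806/507.6) = 0.1601; d = 0.448. Power at 0.45 is 0.80. By t: d = 0.457, power 0.79.
- With exactly 9 per bar (504 staff) the results are 0.295 and 0.449 by z, and 0.301 and 0.457 by t.

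**Step 3: the planned baseline-adjusted model (z).**

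| r, ICC | d, 564 staff | d, 507.6 staff | Power at 0.28 after loss |
|---|---|---|---|
| .50, .10 | 0.282 | 0.289 | 0.77 |
| .10, .05 | 0.283 | 0.293 | 0.76 |
| .10, .10 | 0.324 | 0.333 | 0.65 |
| .50, .05 | 0.246 | 0.255 | 0.87 |
| .30, .05 | 0.271 | 0.281 | 0.80 |

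The first four rows are the extremes of the stated inputs; the last is an interior case. At the extremes, both combinations that give about 0.28 do so on the full sample, and both move to about 0.29 after the loss. At ICC .10 the full range goes from 0.282–0.324 to about 0.29–0.33.

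**The case against.** The case for leaving the sentence alone has several parts.

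- **The shift is small and the starting point is rounded.** Power at 0.28 is already 0.79 by z with every recruit followed. A reader might infer that dropout alone takes a figure with .80 power below it; the arithmetic does not show that. Attrition accounts for about 3 points. This stands.
- **The upper end survives.** By z, 0.45 still has .80 power after the loss, and is in fact nearer the with-attrition value (0.448) than the full-sample one (0.437). No single formula tried returns both stated ends exactly, so the basis of the range is not known. This stands, and limits the point to the lower end.
- **0.28 could come from a calculation with attrition.** A baseline-adjusted model with r = .30 and ICC .05 gives 0.281 after 10% loss. That is possible, but the plan presents 0.28 as the end of a range and .30 is not an end of its correlations. It is therefore too strong to say that 0.28 can arise only without dropout.
- **The planned model may do better.** With baseline adjustment, r = .50 and ICC .05, power at 0.28 after loss is 0.87. This is so, but that combination gives 0.246 on 564 staff and cannot be the source of the stated 0.28.
- **The plan partly covers this.** The mediation sentence gives arm effects on the mediators (0.35 to 0.45) with attrition allowed for, and attitudes, norms, perceived control and intent are themselves individual-level outcomes. Bystander behavior is not covered there.
- **The models accommodate missing data.** They can use incomplete records, but this does not restore the follow-up information that was lost.

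A reader might also go further and infer that the study must recruit more staff, or that the range should be recomputed with whole bars lost. The documents support neither: the plan fixes no single target effect that a shift of 0.01 would miss, and it gives one attrition rate with no mention of bars leaving.

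**Conclusion.** The inconsistency is real and minor. The stated basis of the individual-level range is full enrolment, while the plan's own attrition rate implies about 508 staff at follow-up. On the change-score inputs that reproduce 0.28, the lower end should read about 0.295 by z (0.30 by t), and power at 0.28 is about 0.76 (0.74 by t). The upper end is 0.448 to 0.449 by z and 0.457 by t, which is effectively the 0.45 already stated. These results rest on two-sided alpha .05, equal bar sizes, and loss spread within bars. The omission itself does not depend on the choice between a change score and baseline adjustment, but its consequence at 0.28 does.

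**What to change.** In Power Analysis, apply the 10% attrition to the individual-level sentence and restate the range for about 508 analysed staff, about 9 per bar. Use one formula for both ends: about d = 0.30 to 0.45 (z; 0.295 to 0.449 before rounding up) or 0.30 to 0.46 (t, 54 df) on the change-score inputs. Name alpha and the model. If the range is meant for the baseline-adjusted mixed model in Individual-level Analyses, the corresponding figures at ICC .10 are about 0.29 to 0.33 (z). If the existing range already allows for attrition, say so and give the inputs that produce it.

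The cost is one sentence and a slightly less favourable lower figure. Recruitment, design and analysis stay as they are. A whole-bar-loss scenario could be added, but is optional.
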